[24] Have not had any immunizations, or are not up to date on immunizations recommended by country specific Pediatric guidance	Do not exclude from PPS	Monitor	From monitor’s list.
[29] At Visit 1, have a neutrophil count <1500 cells/ μ L (<1.50 \times 10 ⁹ / μ L or <1.50 GI/L), a lymphocyte count <800 cells/ μ L (<0.80 \times 10 ⁹ / μ L or <0.80 GI/L), a platelet count <100,000 cells/ μ L (<100 \times 10 ⁹ / μ L or <100 GI/L)	Do not exclude from PPS	Monitor and Stats	
Either from monitor’s list, or, If have a neutrophil count <1500 cells/μL (<1.50\times10⁹/μL or <1.50 GI/L), a lymphocyte count <800 cells/μL (<0.80\times10⁹/μL or <0.80 GI/L), a platelet count <100,000 cells/μL (<100\times10⁹/μL or <100 GI/L) or missing at Visit 1.

[32] Previously treated with etanercept	Excluded from PPS	Monitor and Stats	
Either from monitor’s list, or, If have etanercept in the CRFs “Prior Therapy: Psoriasis”.

Important Protocol Deviation Category/Subcategory/Study Specific	Action for PPS Analysis	Source to Identify Protocol Deviation ^a	Statistical Programming Guidance for Clinical Study Report
[33] Have used any therapeutic agent targeted at reducing interleukin-17 (IL-17)	Excluded from PPS	Monitor	From monitor’s list.
[35] Had a live vaccination within 12 weeks prior to Visit 2, or intend to have a live vaccination during the course of the study or within 12 weeks of completing treatment in this study, or have participated in a vaccine clinical study within 12 weeks prior to Visit 2	Do not exclude from PPS	Monitor	From monitor’s list.
Category: Study Procedures			
Subcategory: Violation of Discontinuation Criteria			
[D1] ALT or AST >8× ULN	Do not exclude from PPS	Monitor and Stats	Either from monitor’s list, or, if a patient still receives study treatment after 10 days with confirmed ALT or AST >8× ULN (defined as a test of 8× ULN and a retest within 10 days still >8 × ULN; if not retest, use the test as the confirmed).
[D2] ALT or AST >5× ULN for more than 2 weeks	Do not exclude from PPS	Monitor and Stats	Either from monitor’s list, or, if a patient still receives study treatment after 24 days with confirmed ALT or AST >5× ULN (defined as a test of 5× ULN and a retest within 14 days still >5× ULN; if not retest, use the test as the confirmed).

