[D8] Neutrophil counts <500 cells/μL, or ≥500 and <1000 cells/μL based on 2 test results, or ≥1000 and <1500 cells/μL based on 3 test results and a concurrent infection	Do not exclude from PPS	Monitor and Stats	Either from monitor’s list, or, If a patient still receives study treatment after 10 days with confirmed segmented neutrophil counts <500 cells/μL (defined as a test of <500 cells/μL and a retest within 10 days still <500 cells/μL; if no retest, use the test as the confirmed).
[D9] Total WBC count <2000 cells/μL	Do not exclude from PPS	Monitor and Stats	Either from monitor’s list, or, If a patient still receives study treatment after 10 days with confirmed total WBC count <2000 cells/ μL (defined as a test of <2000 cells/μL and a retest within 10 days still <2000 cells/μL; if no retest, use the test as the confirmed)
[D10] Lymphocyte count <200 cells/μL	Do not exclude from PPS	Monitor and Stats	Either from monitor’s list, or, If a patient still receives study treatment after 10 days with confirmed lymphocyte count <200 cells/μL (defined as a test of <200 cells/μL and a retest within 10 days still <200 cells/μL; if no retest, use the test as the confirmed).

Important Protocol Deviation Category/Subcategory/Study Specific	Action for PPS Analysis	Source to Identify Protocol Deviation^a	Statistical Programming Guidance for Clinical Study Report
[D11] Platelet count <50,000 cells/ μ L	Do not exclude from PPS	Monitor and Stats	Either from monitor’s list, or, If a patient still receives study treatment after 10 days with confirmed platelet count <50,000 cells/ μ L (defined as a test of <50,000 cells/ μ L and a retest within 10 days still <50,000 cells/ μ L; if no retest, use the test as the confirmed).
[D12] Subject BP readings are greater than 95 th percentile at 3 consecutive study visits	Do not exclude from PPS	Monitor	From monitor’s list.
[D13] A severe AE or an SAE, or a clinically significant change in a laboratory value	Do not exclude from PPS	Monitor and Stats	Either from monitor’s list, or, If patient still receives study treatment on the same day or after the date with an AE or SAE.
[D14] Clinically significant systemic hypersensitivity reaction that does not respond to treatment	Do not exclude from PPS	Monitor	From monitor’s list.
[D15] Patient became pregnant	Do not exclude from PPS	Monitor	From monitor’s list.
[D16] Patient developed a malignancy (more than 2 nonmelanoma skin cancers)	Do not exclude from PPS	Monitor	From monitor’s list.

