[D17] Patient has a positive TB test using PPD or QuantiFERON®-TB Gold	Do not exclude from PPS	Monitor	From monitor’s list.
[D18] Change in disease phenotype	Excluded from PPS	Monitor	From monitor’s list.
[D19] Patient requires treatment with another therapeutic agent that has been demonstrated to be effective for the treatment of Ps	Excluded from PPS	Monitor	From monitor’s list.
[D20] Enrollment in any other clinical trial involving an investigational product or enrollment in any other type of medical research judged not to be scientifically or medically compatible with this study	Excluded from PPS	Monitor	From monitor’s list.
[D21] The investigator or attending physician decides that the patient should be withdrawn from the study treatment	Do not exclude from PPS	Monitor	From monitor’s list.

Important Protocol Deviation Category/Subcategory/Study Specific	Action for PPS Analysis	Source to Identify Protocol Deviation^a	Statistical Programming Guidance for Clinical Study Report
[D22] The patient (or guardian) requests to be withdrawn from the study treatment	Do not exclude from PPS	Monitor	From monitor’s list.
[D23] The patient, at any time during the study, scores ≥ 5 for Item 13 on the CDRS-R. Or	Do not exclude from PPS	Monitor and Stats	Either from monitor’s list, or, score ≥ 5 to Item 13 (Suicidal Ideation) of CDRS-R.
[D24] Develops active suicidal ideation with some intent to act with or without a specific plan	Do not exclude from PPS	Monitor and Stats	Either from monitor’s list, or, yes to question 4 or 5 on the “Suicidal Ideation” Portion of C-SSRS.
[D25] Develops suicide-related behaviors as recorded on C-SSRS	Do not exclude from PPS	Monitor and Stats	Either from monitor’s list, or, yes to question “suicidal behavior” on the “Suicidal Behavior” Portion of C-SSRS.
[D26] It is recommended that the subject be assessed by an appropriately trained professional to assist in deciding whether the subject is to be discontinued from the study	Do not exclude from PPS	Monitor	From monitor’s list.
[D27] Investigator or Lilly stopped the patient participation	Do not exclude from PPS	Monitor	From monitor’s list.
Category: Study Procedures			
Subcategory: Excluded Con-meds	Excluded from PPS	Monitor and Stats	Either from monitor’s list, or If patient takes prohibited concomitant medication. Note: Prohibited concomitant medication will be provided by medical in a separate file.
Subcategory: Other			

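### As printed, deviation rows D23-D25 omit the continued-treatment condition and row D2 cannot show an elevation of more than 2 weeks, so compliant subjects can be listed as stopping-rule violators

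*SAP*

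**What the plan says.** Rows D1 to D27 of SAP Table RHCD.6.12 (Section 6.16) form the subcategory for violated discontinuation criteria. The first column names the criterion and the last tells the programmer how to detect it.

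- **D1** is typical of the laboratory rows. It counts a subject "if a patient still receives study treatment after 10 days with confirmed ALT or AST >8× ULN".
- **D13** (severe or serious adverse events, or an important laboratory change) reads "If patient still receives study treatment on the same day or after the date with an AE or SAE".
- **D2** names ALT or AST above 5× ULN "for more than 2 weeks". Its guidance asks for dosing after 24 days with a confirmed elevation, and takes as confirmation a raised test and "a retest within 14 days still >5× ULN; if not retest, use the test as the confirmed".
- **D23** has a label that begins "The patient, at any time during the study, scores", with a threshold of 5. Its guidance gives only that score on "Item 13 (Suicidal Ideation) of CDRS-R".
- **D24** is labelled "Develops active suicidal ideation with some intent to act with or without a specific plan". Its guidance is "yes to question 4 or 5 on the" ideation part of the C-SSRS. D25 is built the same way on the behavior part.

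D2 and D23-D25 can each be identified by the monitor's list or by the program, and footnote a shows the deviation if either source finds it. None of the four removes a subject from the per-protocol set. Section 6.16 plans a by-patient listing and a Period 2 summary by arm, within category and subcategory.

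**The concern.** An entry in this subcategory tells the reader that a child should have stopped study drug and did not. D23-D25 can produce that entry for a child who was stopped at once. D24 and D25 speak of a condition that develops, but set no postbaseline limit. Baseline C-SSRS is collected (the missing-C-SSRS row in the same table shows this), and the same answer at entry already belongs to eligibility row [22]. One baseline answer could therefore appear under two headings.

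D2 can produce an entry for an elevation that was never shown to last as long as the criterion requires. Because either source is enough, a monitor who knows that the subject complied cannot take a programmed flag away.

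What is at stake is the record of site conduct on two sensitive safety rules in a paediatric trial. No efficacy estimate depends on it.

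**Working it through.** **1. Which programmed rows carry a dosing condition (Table RHCD.6.12).** Programmed rows: D1-D11 (11) + D13 (1) + D23-D25 (3) = 15. The other D rows come from the monitor's list alone. All of D1-D11 and D13 require that study drug was still given: 12 rows. D23-D25 do not: 3 rows. D13 counts same-day dosing as well as later dosing.

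**2. D23-D25 applied literally.** A child scores 5 on CDRS-R Item 13, or answers yes to C-SSRS ideation question 4, and receives no further drug. The guidance is met, so the child is listed as a violator.

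**3. What D2 can establish.** The criterion needs more than 14 days. The retest may fall 1 to 14 days after the first test. Permitted intervals longer than 14 days: 0 of 14. A single value that was not retested documents 0 days. The 24 days equals 14 + 10, that is, the 2 weeks of the criterion plus the 10-day allowance used in D1 and D3-D11. It fixes how late a dose must be to count. It does not require the enzyme to be still raised.

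**4. Worked cases for D2.** Laboratory days are illustrative, because the main protocol's laboratory schedule is not among the documents. The Day 56 dose is the Week 8 injection of ixekizumab or placebo; the Day 49 dose in the last row is a weekly etanercept dose. The last column applies the rule proposed under the fix.

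| Values above 5× ULN | Later values | Dose | As printed | Proposed rule |
|---|---|---|---|---|
| Days 28, 31 | normal Days 42, 56 | Day 56 | flagged | not flagged |
| Day 28 | normal Day 35 | Day 56 | not flagged | not flagged |
| Days 28, 42, 45 | none | Day 56 | flagged if 24 days run from the first test | flagged |
| Days 28, 31 | none | Day 56 | flagged | duration not established |
| Days 28, 43 | none | Day 49, then stopped | not flagged | not flagged |

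- First row: 56 − 28 = 28 days from the first test and 56 − 31 = 25 days from the retest, so the 24-day clause is met from either start. The documented elevation is 31 − 28 = 3 days. A normal value follows 42 − 28 = 14 days after the first raised test, so from that test the elevation did not exceed 2 weeks.
- Third row: 45 − 28 = 17 days, which exceeds 14, and the dose falls 28 days after the first test and after Day 45.
- Last row: 49 − 28 = 21 days, inside the 24-day limit, so the proposed rule keeps the 10-day allowance.

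**5. Largest effect of one false flag on the Period 2 subcategory percentage.** Planned sizes are from SAP Sections 5.2.1 and 5.2.2: 1/110 = 0.9 points for ixekizumab, 1/55 = 1.8 for placebo, 1/30 = 3.3 for etanercept. If the subject is already in the subcategory, the effect is 0. D13's guidance, as printed, takes in any subject dosed on or after the date of an adverse event, so many subjects would already be there.

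**The case against.** **The subcategory title may supply the missing condition.** The first column lists triggers, the title says violation, and footnote a leaves detailed programming to an ADaM specification. On that reading, adding a dosing condition to D23-D25 is elaboration. This stands in part: the specification is not supplied and may already do it. But the other twelve programmed rows state the condition, so its absence from three reads as an omission. D2 is different, since its printed confirmation rule would have to be changed.

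**D2's 24 days may mean 24 days of elevation.** The phrase can be read so, but the parenthesis then defines confirmation by a retest within 14 days or by one value, and nothing enforces persistence.

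**A normal value inside the window should clear the subject.** A normal first retest does. In the first worked case, the Day 42 value might also clear it on a strict reading. Move that value to Day 43 and the case is flagged even then, on 3 documented days. Duration is then unproven rather than disproved, because 43 − 28 = 15.

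**Other outputs let a reader check.** This stands. Table RHCD.6.7 plans a listing of subjects with ALT or AST at 3× ULN or more, with values by visit and treatment start and stop dates. CDRS-R (Section 6.14.7), C-SSRS (Section 6.14.8) and study-drug administration (Section 6.9) are listed by patient. They allow an entry to be checked but do not correct it.

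**Over-inclusive screening is defensible in children.** It is for a review list. It is not for a table whose title states that a rule was broken.

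**Conclusion.** The point holds for the printed guidance and is minor. D23-D25 list subjects on a score or answer alone. D2 can flag an elevation not shown to last more than 2 weeks. The effect is confined to the important-deviation listing and the Period 2 summary. Section 6.14.8 expects few or no suicidality events, no rate is given for D2, and D13's breadth makes the net change in the subcategory percentage likely close to zero.

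A reader might infer three stronger things that the documents do not support:

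- That the delivered listing will contain false violators. The ADaM specification is not available, and there may be no such events.
- That the comparison of deviation rates between arms will be materially distorted. The figures in step 5 are ceilings for one subject, not expected shifts.
- That the per-protocol or efficacy results are affected. None of the four rows excludes anyone from the per-protocol set.

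The conclusion takes the criteria from the table's first column, because the main protocol's stopping rules are not supplied. Row D26 suggests that a suicidality finding may lead first to a professional assessment. If so, a flag on the answer alone is weaker evidence still.

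**What to change.** - **D23-D25:** add that study treatment was given later on the same day as the qualifying assessment, or on any day after it. A condition limited to later days would miss a child injected after a positive answer at the same visit.
- **D24-D25:** use postbaseline assessments only. Flag baseline positives by program under eligibility row [22], changing its source from the monitor alone to monitor and program, so that none is lost. D23 needs no such limit, because its label covers the whole study.
- **D2:** flag when values above 5× ULN are documented on tests more than 14 days apart, with no value at or below 5× ULN between them, and study drug was given more than 24 days after the first such value and after the confirming test.
- **D2, unresolved cases:** list separately, as 'duration not established', subjects dosed past 24 days with no retest, or whose only retests before that dose fall within 14 days and are all above 5× ULN.
- Keep the either-source rule.

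The cost is the wording of four rows, one change of source, minor programming and one short extra list. The table was already revised in SAP Versions 2 and 3 (Section 3). The same-day rule needs the order of dose and assessment. The administration log records dose time (Section 6.9), but the documents do not say whether assessment time is captured.

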[D3] ALT or AST >3× ULN and TBL >2 × ULN or prothrombin time >1.5 time ULN	Do not exclude from PPS	Monitor and Stats	Either from monitor’s list, or, if a patient still receives study treatment after 10 days with confirmed ALT or AST >3× ULN and TBL >2× ULN or prothrombin time >1.5× ULN (defined as a test of 3× ULN and 2× ULN or 1.5× ULN and a retest within 10 days still >3× ULN and 2× ULN or 1.5× ULN; if not retest, use the test as the confirmed).
[D4] ALT or AST >3× ULN with the appearance of fatigue, nausea, vomiting, right upper-quadrant pain or tenderness, fever, rash, and/or eosinophilia (>5%)	Do not exclude from PPS	Monitor and Stats	Either from monitor’s list, or, If a patient still receives study treatment after 10 days with confirmed ALT or AST >3× ULN with the appearance of fatigue, nausea, vomiting, right upper-quadrant pain or tenderness, fever, rash, and/or eosinophilia (>5%) (defined as a test of 3× ULN and a retest within 10 days still >3× ULN; if not retest, use the test as the confirmed).

Important Protocol Deviation Category/Subcategory/Study Specific	Action for PPS Analysis	Source to Identify Protocol Deviation ^a	Statistical Programming Guidance for Clinical Study Report
[D5] ALP >3× ULN	Do not exclude from PPS	Monitor and Stats	Either from monitor’s list, or, If a patient still receives study treatment after 10 days with confirmed ALP >3× ULN (defined as a test of 3× ULN and a retest within 10 days still >3× ULN; if not retest, use the test as the confirmed).
[D6] ALP >2.5× ULN and TBL >2× ULN	Do not exclude from PPS	Monitor and Stats	Either from monitor’s list, or, If a patient still receives study treatment after 10 days with confirmed ALP >2.5× ULN and TBL >2× ULN (defined as a test of 3× ULN and 2× ULN and a retest within 10 days still >3× ULN and 2× ULN; if not retest, use the test as the confirmed).
[D7] ALP >2.5× ULN with the appearance of fatigue, nausea, vomiting, right upper-quadrant pain or tenderness, fever, rash, and/or eosinophilia (>5%)	Do not exclude from PPS	Monitor and Stats	Either from monitor’s list, or, If a patient still receives study treatment after 10 days with confirmed ALP >2.5× ULN with the appearance of fatigue, nausea, vomiting, right upper-quadrant pain or tenderness, fever, rash, and/or eosinophilia (>5%) (defined as a test of 2.5× ULN and a retest within 10 days still >2.5× ULN; if not retest, use the test as the confirmed).

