The term “Stats” indicates the protocol deviation will be programmed based on data in clinical database by statistical programmers with the statistical programming guidance provided as the last column. The detailed programming specification will be documented in Analysis Data Model (ADaM) specification.

The terms “Monitor and Stats” indicates the protocol deviation will be a combination of monitor’s list (SDTM.DV domain) and statistical programming from clinical database, the deviation will show if either source identifies.

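### In the SAP's deviation table, the programmed checks for two stopping-rule rows (D6 and D8) cover less than the rows' own labels

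*SAP*

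**What the plan says.** Table RHCD.6.12 (SAP Section 6.16) gives each important deviation a label, a PPS action, a source and, in its last column, programming guidance. Footnote a explains the sources. Deviations assigned to Stats are programmed from the clinical database "with the statistical programming guidance provided as the last column". For rows assigned to both Monitor and Stats, "the deviation will show if either source identifies". The footnote also says: "The detailed programming specification will be documented in Analysis Data Model (ADaM) specification".

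- **D6** (both sources). The label is ALP >2.5× ULN with TBL >2× ULN. The guidance flags continued dosing after 10 days with "confirmed ALP >2.5× ULN and TBL >2× ULN (defined as a test of 3× ULN and 2× ULN", and the retest must still exceed 3× for ALP.
- **D5** (both sources). The guidance flags continued dosing after 10 days with "confirmed ALP >3× ULN (defined as a test of 3× ULN and a retest within 10 days still >3× ULN".
- **D8** (both sources). The label has three alternatives: below 500 cells/μL; 500 to below 1000 on two results; and 1000 to below 1500 "based on 3 test results and a concurrent infection". Apart from the monitor's list, the guidance has one rule: "a patient still receives study treatment after 10 days with confirmed segmented neutrophil counts" below 500, with a retest within 10 days (or the single test if there was no retest).

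Neither D6 nor D8 removes a patient from the PPS.

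**The concern.** Section 6.16 counts as important those deviations that may significantly affect a subject's rights, safety or well-being. Dosing a child past a liver or neutropenia stopping criterion fits that description. Where a row has two sources, the programmed one is the safeguard if the monitor's list misses a case. In D6 the safeguard is set at the wrong threshold. In D8 the SAP states it for one criterion of three. At stake is whether the important-deviation summary (Period 2, ITT Population) and the by-patient listing are complete.

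**Working it through.** No power, alpha or sample-size figure is involved, so the check sets labels against guidance.

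**Step 1: D6 against its label, D5 and D7.** Take TBL at 2.5× ULN, the same ALP on test and retest, and dosing continuing beyond 10 days. The ALP values are illustrative.

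| ALP (× ULN) | Meets D6 label (>2.5) | D6 as written (retest >3) | D6 confirmed at 2.5 | D5 (retest >3) |
|---|---|---|---|---|
| 2.6 | yes | no | yes | no |
| 2.8 | yes | no | yes | no |
| 3.0 | yes | no | yes | no |
| 3.1 | yes | yes | yes | yes |

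The stated rule finds 0 of the 3 cases above 2.5× and up to 3×; a 2.5× confirmation finds all 3. D6 as written is D5's ALP condition plus a bilirubin condition, so its flagged patients are a subset of D5's. D7 has the same ALP label threshold (with symptoms in place of bilirubin) and confirms at 2.5×.

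**Step 2: D8 criterion by criterion.**

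| Label criterion (cells/μL) | Programmed rule in SAP | Monitor's list |
|---|---|---|
| <500 | yes, confirmed | yes |
| ≥500 and <1000, 2 results | none stated | yes |
| ≥1000 and <1500, 3 results, concurrent infection | none stated | yes |

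One of three criteria has a programmed rule. Sections 6.14.4.1 and 6.14.4.2 cover shift categories and neutrophil recovery, not dosing continued after a criterion was met.

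**Step 3: how isolated this is.** Rows with both sources under the discontinuation criteria are D1 to D11 (11), D13, and D23 to D25 (3): 11 + 1 + 3 = 15. Setting aside the retest conditions that many rows add, 3 of the 15 leave out part of their label: D6, D8 and D13. D13 omits only a clinically significant laboratory change, which needs medical judgement, so it is not pressed here.

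**Step 4: whether upper limits alone would do for D8.** Suppose the added checks used only <1000 (two results) and <1500 (three results with infection). Take three-result runs of 450, 700, 1200 or 1800, with and without infection. Runs that meet no D8 criterion as labelled contain no 450 and at most one 700:

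- no 700: 2³ = 8 runs
- one 700: 3 × 2² = 12 runs
- total: 20 runs × 2 infection states = 40
- less 1200-1200-1200 with infection, which meets the third criterion: 39

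Upper limits alone would flag 3 of these 39: one 700 and two 1200s, in any of three orders, with infection. That wording goes beyond the label. This tests wording only and says nothing about incidence.

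**The case against.** The strongest reply concerns D8. A row with both sources is a union, and the footnote does not promise that each source covers every part of the label. The table leaves other programmable criteria to monitors, notably D12 (blood pressure above the 95th percentile at three consecutive visits). Giving the simple threshold to programmers and the multi-result rules to monitors is a plausible design. The concurrent infection in the third criterion needs a window that the SAP does not define. The split may be set in the Trial Issue Management Plan, which the revision history names as the basis for this table, or completed in the ADaM specification; neither is supplied. There is also other visibility: neutrophil shift tables in bands (6.14.4.1), a listing of treatment administration (6.9), and review of infections against haematology parameters (Table RHCD.6.7). D13, read literally, flags anyone who "still receives study treatment on the same day or after the date with an AE or SAE", which could include a patient with an infection, though not as neutropenia.

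Much of this stands. It rules out calling D8 a contradiction, and it makes a monitor-only intent possible. But rows meant to be monitor-only, such as D12 and D14 to D16, are marked that way, and D8 is not. Row [29] already programs a neutrophil check below 1500 at Visit 1. The shift tables show counts and the administration listing shows dosing; neither shows dosing continued past a criterion.

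For D6, the reply is that the operative phrase already says 2.5× and the 3× looks like carry-over from D5. That explains the slip but does not remove it, because the parenthesis defines what counts as confirmed.

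A reader might also infer that affected children would go undetected, that the final code is wrong, or that the PPS is contaminated. The documents support none of these: the monitor route remains for every criterion, the code specification is not supplied, and both rows leave the PPS unchanged.

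**Conclusion.** The point holds as a mismatch between label and stated programming rule in two rows. D6 is a wrong confirmation threshold: it misses ALP above 2.5× and up to 3× ULN and adds no patient to those D5 flags. D8 states a programmed rule for one criterion of three; as far as the SAP states, the other two depend on the monitor's list.

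The consequence is possible under-reporting in the important-deviation summary and listing. The documents give no frequency for these events and no detection rate for monitors, so the number of missed cases cannot be estimated and may be zero. There is no PPS or efficacy effect. The conclusion rests on reading the last column as the programming rule, as footnote a says, and on the SAP text alone. It should be corrected, but it does not threaten the trial's conclusions.

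**What to change.** **D6:** change the ALP value in the confirmation definition from 3× to 2.5× ULN, for both test and retest, matching D7.

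**D8:** keep the <500 check and do one of two things.

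- Add programmed checks for continued dosing after two results ≥500 and <1000 cells/μL, and after three results ≥1000 and <1500 cells/μL with a concurrent infection adverse event. The Infections and infestations SOC definition in Table RHCD.6.7 can serve for the latter. Take result spacing, retest and infection windows, and the handling of runs that cross bands from the discontinuation rule in the main protocol, which is not among the documents supplied. Do not drop the lower limits unless that rule supports it.
- Or state in the row that these two criteria are identified by monitors only.

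The cost is two table cells, a few lines of code on laboratory, adverse-event and exposure data already held, and one check against the main protocol. The deviation count may rise. It would also be another edit to this table, possibly after the primary lock. There is precedent: SAP Version 3 was approved after that lock, and the only change it lists is to this table.
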